3.2 Investigationa l Product (t reatment, de vice) and Indic ation

(ICH/E6 6.2.1; AGEK 2; SPIRIT #6)

ICH: Name and descripti on of the investigational product(s).

All investigational products are CE-labelled MDs. All MDs (hearing instruments with respective hearing instrument software and acoustic couplings, fitting software and wireless accessories) are bearing product names and unique serial numbers for an unambiguous assignment and retracing of the product to the subject. State of the art methods may be used to verify the fitting of the hearing systems (e.g. Real Ear Measurements [12]).

Hearing Instruments:

In general, the hearing instruments themselves can be separated in different form factors: In-The-Ear (ITE), Invisible-In-Canal (IIC), Receiver-In-Canal (RIC) and Behind-The-Ear (BTE) including different acoustic couplings depending on the hearing loss and on the anatomical conditions of the hearing instrument user.

Hearing Instrument Software:

The hearing instrument software comprises the operating system and the signal processing of a hearing instrument. It contains the algorithmic approaches and can be operated in a respective hearing instrument.

Acoustic coupling:

Together with a BTE or RIC, the acoustic coupling (e.g. earpiece) is a system which is also a medical device. Without the merge of the acoustic coupling and hearing instrument the earpiece has no medical harness.

Fitting Software:

The hearing instruments will be set and fine-tuned to the individual hearing loss and needs of the subject by using the corresponding fitting software in accordance to the specialised information whereof the latest version can always be printed out (e.g. of the Phonak Fitting Software).

Wireless Accessories:

The Sonova brand Wireless Accessories comprise various solutions to simplify the volume adjustment as well as the program switching in a hearing instrument but also to enhance speech intelligibility in noisy environments, in making phone calls or in bridging distances between a talker and the hearing instrument user like in class/conferences/lectures. The subsequent current Sonova brand Wireless Accessory solutions are also MDs. They also have a unique serial number for an unambiguous assignment and retracing of the product to the subject. The intended purpose is also according to the instruction manual.

3.3 Preclinic al Evidence

(ICH/E6 6.2.2; SPIRIT #6a)

ICH: A summary of findings from nonclinical studies that potentially have clinical significance

For MD this entry is only applicable if needed for pre-marketed/marketed devices needing Swissmedic notification (Guidance on the biological evaluation of medical devices is given in ISO 10993). Therefore, this entry is not applicable for this study.

3.4 Clin i cal Evidence to Date

(ICH/E6 6.2.2; SPIRIT #6a)

ICH: A summary of findings from ... and from clinical trials that are relevant to the trial.

There is no available clinical research data to date on the investigational product.

3.5 Dose Rationale / Medical Device: Rationale for the intended purpose in study (pre-market MD)

(ICH/E6 6.2.4; SPIRIT #6a)

ICH: Description of and justification for the route of administration, dosage, dosage regimen, and treatment period(s).

The hearing instruments will be set and fine-tuned to the individual hearing threshold and needs of the subject in accordance to established audiological test methods and according to the best knowledge and conscience of trained staff to promote new developments.

3.6 Explanation for choice of comparator (or placebo)

(AGEK 11.3; SPIRIT #6b)

To investigate the effect of the sound changing principles in hearing instruments, different parameter settings of the respective application will be compared. This may include a setting in which the sound changing principle is disabled (switched off). If applicable the novel sound changing principle will be compared with those used in previous hearing instruments. Depending on which application will be compared the number of comparators may differ.

3.7 Risks / Benefits

(ClinO, Appendix 4, 3.5; Art 25d2; ICH/E6 6.2.3; AGEK 11.1; SPIRIT #6a; MD: ISO 14155 Annex A & ISO 14971)

ICH: Summary of the known and potential risks and benefits, if any, to human subjects.

Risks regarding the Investigational device (MD).

1. Infections can be caused by injuries of the ear canal which can occur by the placement of the acoustic coupling (e. g. receiver, earpiece) to the outer ear canal or by the placement of an ITE or IIC device. Therefore, the ear canal will be thoroughly checked and assessed during the study.
2. Pressure points can be caused by the hearing instrument or the acoustic coupling. In case of pressure points, the hearing instrument should not be worn until it healed up. The cause of the pressure point would then be investigated.
3. Tinnitus can be caused by wearing of the hearing instrument. An existing tinnitus can be temporarily amplified. If the tinnitus doesn't improve after several days of not wearing the hearing instrument, an assessment with an independent doctor (ENT) is necessary.
4. A headache can occur, especially for new hearing instrument users. If a headache appears, the subject is instructed to interrupt the hearing instrument use until the audiologist applies a new fitting (e.g. reduced gain level) to acclimatize the subject to the devices.
5. The hearing instrument can reach a high maximum power output (MPO). The MPO will be set accordingly to clinical expertise at a level that no injuries can occur.

Risks regarding the involved procedures.

1. Used Loudspeakers or Headphones can reach high maximum power outputs. Only standard Loudspeakers and Headphones having a limited maximum power output will be used.
2. Study appointments might be tiring for the subjects, therefore regular pauses will be done during the appointments.

Benefits of the study.

1. Participating subjects learn something new about their own hearing.
2. Participating subjects are fitted with the latest hearing system products and have the opportunity to try it out during the study period.
3. Participating subjects acquire knowledge about how she/he can be served audiology.
4. Gained knowledge about novel and innovative sound changing principles will drive further development to provide audiologically meaningful and useful solutions for hearing impaired end-users.

4. STUDY OBJECTIVES

(ICH/E6 6.3; AGEK 3; SPIRIT #7)

ICH: A detailed description of the objectives and the purpose of the trial.

This section includes a description of the overall, primary and secondary objective(s) of the study.

4.1 Overall Objective

This study is the overall summation of a series of several sub-studies concerning the evaluation of novel sound changing principles in hearing instruments over the next 10 years. These novel sound changing principles are continuously developed and improved in the mentioned time frame. For each sound changing principle a separate study (sub-study) will be conducted. All of these sub-studies pursue the goal to investigate strength and weaknesses of the respective novel sound changing principle.

The overall objective is to investigate the audiological performance for each of these sound changing principles on hearing impaired subjects using respective hearing performance outcome measures. The results are assessed in reference to those from sound changing principles used in recent hearing instruments and/or with the sound changing principle disabled.

4.2 Primary Objective

The primary objective of each study is to determine and assess the benefit of these novel sound changing principles for their intended use in terms of the associated hearing dimension (speech intelligibility, signal clarity and sound quality / hearing comfort) respectively. Depending on the aim of the respective sound changing principle the associated hearing performance outcome measure will be

chosen. Furthermore different parameter adjustments of the novel sound changing principle will be examined to determine the most useful setting. The results are assessed in referenced to those from sound changing principles used in recent hearing instruments and/or with the sound changing principle disabled.

4.3 Secondary Objectives

The secondary objective is to investigate and assess the effect of the respective sound changing principle in real world environment. The results are assessed in referenced to those from sound changing principles used in recent hearing instruments and/or with the sound changing principle disabled.

4.4 Safety Objectives

N/A

5. STUDY OUTCOMES

(ICH/E6 6.4.1; AGEK 4.1; SPIRIT #12)

ICH: A specific statement of the primary endpoints and the secondary endpoints, if any, to be measured during the trial.

This section includes a description of the outcomes of the study including the specific measurement variable and analysis metric.

5.1 Primary Outcome

The primary outcomes are the laboratory test results. These tests intend to evaluate the hearing performance in terms of speech intelligibility, signal clarity and sound quality / hearing comfort. With help of the received data from these outcome measurements it can be concluded whether the experimental condition is superior to the comparator with regard to hearing performance.

Each sub-study focuses specifically on one of these hearing dimensions. The corresponding other hearing dimensions may be additionally examined to investigate a trade-off (e.g. trade-off for speech intelligibility versus sound quality / hearing comfort). Depending on the investigational sound changing principle and the corresponding focused feature or function (aim) the appropriate audiological testing method will be chosen (Table 4).

Table 4: Audiological testing methods for outcome measures in the laboratory

Performance	Aim	Method	Result [unit]
Speech intelligibility	Assessment of speech intelligibility in quiet	Freiburger Sprachtest [13]	Discrimination [%]
	Assessment of speech intelligibility in noise	Oldenburger Satztest (OLSA) [14, 15]	Speech intelligibility threshold in noise [dB SNR]
	Assessment of speech intelligibility in quiet or in noise	Einsilber-Reimtest nach von Wallenberg und Kollmeier (WaKo) (quiet/noise) [16]	Discrimination [%]
	Assessment of speech intelligibility in quiet or in noise	Göttinger Satztest (GöSa) (quiet/noise) [17]	SRT in quiet [dB], in noise [dB SNR]
	Assessment of speech intelligibility with variable target location and talker identity	Coordinate Response Measure [18, 19, 20]	SRT [dB] or performance level (%-correct responses)
	Assessment of cognitive influences on speech perception	Cognitive Measures, e.g. for Working-Memory Capacity (e.g., Reading Span [21]), Executive Functioning and Attention (e.g., Stroop Task), Overall Cognitive Ability (e.g., MoCA [22])	Performance Level [%-correct responses or time-to-complete outcomes]
	Objective Assessment of Listening Effort and Spare Capacity	Response Delays during above listed Speech Intelligibility Tests; Dual-Task Paradigms with Speech Intelligibility as primary task and a Cognitive Outcome Measure as the Secondary Add-On Task (e.g., Assessment of Cognitive Capacity for tasks of Selective Attention or Working Memory during the Primary Task [23, 24, 25])	SRT [%] and Errors [%] or Response Times [ms]
Signal Clarity	Determination of hearing threshold of pure tones	Pure Tone Audiometry [26]	Yes/No replies
	Determination of threshold of fricatives	Phoneme Perception Test (PPT) [Error! Reference source not found. - 29]	Detection, Distinction and Recognition Threshold [dB SPL]
	Determination of localization capabilities with and/or without hearing systems	Localization Test in Quiet, Noise, Reverberation. [31]	Average RMS localization error ['], back-front confusions [%]
	Assessment of music perception	Adaptive Music Perception Test [32]	Detection Threshold
Sound Quality / Hearing Comfort	Qualitative description	Interviews: Qualitative and Quantitative (ad hoc list of questions, semi-standardized, standardized or normed), Focus Groups [43]	Narrative, open/closed replies, ranking, single/multiple choice, or point on a rating scale
	Assessment of sound quality	Subjective Rating Scale [33, 34]	Point on a scale

	Judgment which of the entities in pairs is preferred or has a greater amount of some quantitative property	Paired Comparison [35]	Preference or point on a scale
	Subjective evaluation of the audio quality of a defined sound	Multi-Stimulus Test with Hidden Reference and Anchor (MUSHRA) [36]	Point on a scale
	Quantitative assessment of a person's perception of facts or circumstances regarding hearing system	Semantic Differential Analysis/ Polarity Profile [37]	Point on a scale
	Assessment of a person's perception of a specific listening situation through selected hearing systems or hearing aid programs	Simulations of Various Listening Situations (in Car/Cafeteria/Reverberation) via Loudspeakers including Preference Rating or Subjective Rating Scale	Preference or point on a scale
	Determination of acceptable noise intensities while listening to speech	Acceptable Noise Level (ANL) Test [38, 39]	Tolerated SNR [dB]
	Assessment of the subjectively perceived loudness of a test signal	Categorical Loudness Scaling [40]	Loudness [CU]
	Assessment of a hearing aid user's affection by objective occlusion (closed ear canals)	Occlusion Measurement and Leakage Measurement using REM method [41]	Frequency Responses [magnitude and phase of the output as a function of frequency] => Level differences [dB] and Level Loss [dB]

5.2 Secondary Outcome s

The secondary outcomes are the subjective test results and comments gathered in real world environment (e.g. during guided walks) and with questionnaires during the home trials. Depending on the investigational sound changing principle and the corresponding focused feature or function (aim) the appropriate audiological testing method will be chosen. A collection of possible methods is listed below (Table 5).

Table 5: Audiological testing methods for outcome measures in real world environment

Performance	Aim	Method	Result [unit]
Subjective test in real world environment	Subjective Assessment of Listening Effort and Hearing Fatigue	Questionnaires about Listening Effort in Everyday Life (e.g., CTO [42]), Rating Scales of Effort perceived during above listed Audiological Tests	Score on a Continuous Rating Scale or on a Likert Rating Scale
	Assessment of system stability	Quantitative Questionnaires [43]	Yes/No replies and open-ended
	Assessment of real-time individual information regarding hearing system and/or listening situation via Phonak App on Smartphone in daily life	MobEval [44, 45, 46]	Logging of predefined HI parameters, time [h/min/s], open/closed replies or single/multiple choice
	Survey of audibility of distortions, artefacts, interruptions, feedback, system noise or other malfunctions	Quantitative Questionnaires [43]	Yes/No replies and open-ended
	Determination of individual information or circumstances regarding hearing system and/or listening situation	Interviews: Qualitative and Quantitative (ad hoc list of questions, semi-standardized, standardized or normed), Focus Groups [43]	Narrative, open/closed replies, ranking, single/multiple choice, or point on a rating scale
	Measurement of self-reported auditory disability across a wide variety of domains, reflecting the reality of hearing in the everyday world	The Speech, Spatial and Qualities of Hearing Scale (SSQ) [47]	Score on a Continuous Rating Scale

5.3 Other Outcomes of Interest

Other outcomes of interest are potential side effects and informal feedback from the subjects regarding subjective rating of the performance. Additionally further measures (e.g. regarding psychoacoustic function) may be used to determine the individual hearing abilities and/or compare and correlate these results with the ones from the primary outcomes (Table 6Table 6:).

Table 6: Additional further measures

Performance	Aim	Method	Result [unit]
Auditory function	Assess Psychoacoustic measures	Basic psychoacoustic measurements (e.g. ITD/IPD/ILD, JNDs, BMLDs, frequency discrimination thresholds, measures of frequency selectivity, frequency modulation detection), Tinnitus pitch and loudness matching, TEN (Threshold-Equalizing-Noise) Test [48 - 51]	Detection threshold
Behavioural observations	Observation of behaviour during the test session	Video analysis, recordings, motion- and position sensor, reaction time measurement	Analysis of respective observation method
Peripheral psychophysiological observations	Assess Peripheral psychophysiological measures	HEG (hemoencephalography), EEG (electroencephalography), ECG (electrocardiogram), EMG (electromyography), EDA (Electro Dermal Activity or Galvanic Skin Response), Respiratory rate, Pulse rate, Pupillometry [52 – 54]	Respective result of peripheral psychophysiological measure

5.4 Safety Outcomes

N/A

6. STUDY DESIGN

(ICH/E6 6.4; AGEK 4; SPIRIT #8)

This section describes the design of the study and its rationale, the type, allocation ratio and framework.

6.1 General study design and justification of design

(ICH/E6 6.4.2, 6.4.5; AGEK 4.2; SPIRIT #8)

ICH: The scientific integrity of the trial and the credibility of the data from the trial depend substantially on the trial design.

ICH: A description of the type/design of trial to be conducted (e.g., double-blind, placebo-control led, parallel design) and a schematic diagram of trial design, procedures and stages.

ICH: The expected duration of subject participation, and a description of the sequence and duration of all trial periods, including follow-up, if any.

A methodical evaluation of novel sound changing principles in CE-Labelled Sonova brand hearing instruments (primarily Phonak hearing instruments) is intended to be conducted on hearing impaired and normal hearing subjects. This will be a controlled, single blinded (participants), randomised (sequence of test procedure and sequence of tested setting/device), cross-over (investigational product/setting) active comparator study which will be conducted mono centric at Sonova AG Headquarters based in Stäfa.

Treatments/Interventions:

Hearing systems (hearing instruments with hearing instrument software and respective acoustic coupling, fitting software and wireless accessories). All CE labelled MDs.

Population:

Adult participants with different degrees of hearing abilities. In the pre-studies it is planned to include up to 5 participants. The main studies will normally include 20 - 25 participants each. If possible a power analysis is carried out for each study to determine the necessary number of subjects.

Level and method of blinding/masking:

The tests will be at least single blinded.

When testing different parameter settings of the novel application and/or comparing novel with previous applications whereas these approaches are available as optional settings in one hearing instrument, the subjects will not know which setting is activated during the respective testing.

In cases where these settings are not accessible in one hearing instrument (e.g. previous sound changing principle is not supported by the latest hearing instrument technology any more), the test needs to be undertaken with several (two) separate hearing instruments, whereas the housing of these hearing instruments may differ. The subjects will not be informed about the setting or the sound changing principle in the specific hearing instrument.

If possible double blinding will be accomplished with help of computer controlled testing procedures (e.g. software tool for MUSHRA test).

Kind of comparators:

The comparators are different parameter setting of novel sound changing principles in recent hearing instrument (this may include a setting in which the sound changing principle is switched off) as well as sound changing principles in previous hearing instruments.

Method of assignment to treatment/intervention:

This study will be a controlled cross-overs study. Each subjects will receive the intervention to be tested (hearing systems with novel sound changing principles) as well as the respective comparator and serves therefore as his or her own control. The order of the investigational settings and/or products will be randomized. For home trials a respective wash-out period of one week is considered and applied if possible and meaningful.

Sequence of duration of all study periods:

The studies shall take place within the timeframe from 01.07.2016 to 30.06.2026 after approval by CEC. Each study part will take about 6 months and may overlap with other sub studies. The detailed duration of the appointments are listed in the study schedule.

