6.2.2 Blinding procedures

Trial participants will be blinded after assignment to interventions. The subjects will not know which hearing instrument technology they are wearing or which hearing instrument setting is activated during the respective testing (Please refer to section 6.1 General study design and justification of design). If possible double blinding will be executed with help of computer controlled testing procedures (e.g. software tool for MUSHRA Test).

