8.1.2 Control Intervention (stan dard/routine/com parator treatment / medical device)

ICH: Name and descripti on of the investigational product(s).

Same as in 8.1.1, whereas the respective sound changing principle is disabled (switched off or switched to a parameter setting with weakest effect) as well as previous hearing instrument technology (containing comparable previous sound changing principles).

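### Participant blinding is claimed for all tests, but is neither secured nor checked where two instruments with different housings are compared

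*Combined protocol and SAP*

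**What the plan says.** The general claim in section 6.1 is "The tests will be at least single blinded". Section 6.2.2 extends it to devices as well as settings: "The subjects will not know which hearing instrument technology they are wearing or which hearing instrument setting is activated during the respective testing". It refers the reader back to section 6.1 but states no exception.

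Section 6.1 separates two situations. If the settings are all available in one instrument, participants do not know which is active. If they are not, two separate instruments are used, "whereas the housing of these hearing instruments may differ". The safeguard for this second situation is: "The subjects will not be informed about the setting or the sound changing principle in the specific hearing instrument".

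Section 6.2.3 adds that participants receive little product information, and that fit, comfort and ease of operation are checked so that form factor does not bias the results. Double blinding is planned only where possible, through computer-controlled tests.

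Section 8.1.2 makes previous-generation technology a planned control. It also allows a control within the same device, in which "the respective sound changing principle is disabled (switched off or switched to a parameter setting with weakest effect").

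**The concern.** Withholding information is not the same as masking. A participant who sees and handles two differently shaped instruments knows that they differ, and may work out which belongs to the newer generation. Section 3.2 says that the devices carry product names and serial numbers, and nothing says that these are covered. Section 6.2.3 has participants put the devices on, change batteries and switch them on and off. Section 3.8 allows sponsor employees who may work on innovation projects, and section 7.1 allows experienced hearing aid users. Section 3.7 lists as a benefit of taking part that "Participating subjects are fitted with the latest hearing system products", so a belief that newer is better is foreseeable.

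The outcomes most open to such a belief are ratings and preferences. Under Sound Quality / Hearing Comfort, Table 4 in section 5.1 lists rating scales, paired comparison and preference ratings among the laboratory tests, and laboratory test results are the primary outcomes. Section 9.2.1 says that these data show whether the experimental condition is superior. If participants recognise the newer device, part of a rating advantage could be expectation, and the report would have no means of telling.

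**Working it through.** **Setting the sections side by side**

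1. Claim: at least single blind for all tests (6.1); technology unknown to the wearer (6.2.2).
2. Exception in practice: two instruments, possibly with different housings (6.1).
3. Protection in that exception: participants are not told (6.1), little product information is given (6.2.3), and comfort and handling are checked (6.2.3). None of these prevents recognition by sight or touch.
4. Not found anywhere: matched or covered housings, a record of participants' guesses, or separate labelling of cross-device results.
5. Randomised order (6.2.1) balances order effects. It does not remove a preference that follows the device.

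The claim in step 1 is therefore wider than steps 3 and 4 can support.

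**Illustration of size**

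The plan gives no figure to reproduce: section 11.2 states 20-25 participants with no effect size, SD or power.

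- From the documents: n = 20 or 25 (11.2); within-subject comparison (6.1); 5% significance level (11.4), with sidedness not stated.
- Assumed: a two-sided paired t-test, no true difference, and an expectation shift of b SDs of the within-subject difference in favour of the newer device.
- Formula: the probability of a significant result in favour of the newer device is P(T > t(0.975, n-1)), where T follows a noncentral t distribution with n-1 degrees of freedom and noncentrality b√n.
- For b = 0.2, the noncentrality is 0.2 × √20 = 0.894 at n = 20 and 0.2 × √25 = 1.0 at n = 25.

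| Assumed shift b | n = 20 | n = 25 |
|---|---|---|
| 0 | 2.5% | 2.5% |
| 0.1 | 6.2% | 6.9% |
| 0.2 | 13.3% | 15.9% |
| 0.3 | 24.6% | 30.2% |
| 0.5 | 56.4% | 67.0% |

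Counting both directions, b = 0.2 gives 13.6% and 16.1%, against 5% nominal. For scale, the standardised difference detectable with 80% power is 0.66 at n = 20 and 0.58 at n = 25. A shift of 0.2 is thus about a third of that (0.2/0.66 = 0.30; 0.2/0.58 = 0.34). Section 11.4 also allows a Wilcoxon test, for which the figures would differ somewhat.

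**The case against.** The plan discloses the housing problem itself. For cross-device tests, section 6.1 promises only that participants will not be informed; the flat promise about not knowing is kept there for settings within one instrument. Section 6.2.3 adds partial measures and mentions subjective results specifically. This stands as credit to the plan, but it does not rescue the unqualified sentence in 6.2.2 or the general sentence in 6.1.

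A reader might infer that blinding is lost in every cross-device comparison. The documents do not support that. Housings only may differ, and a different housing shows that two devices are not the same, not which is novel. For participants without device knowledge, blinding is weakened and unverified rather than certainly broken. The benefit listed in 3.7 does not show that participants are told which device is the latest.

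A reader might also apply the error rates to everything the sub-studies measure. Section 11.2 says that the real-world objective is handled mainly descriptively, so a false-superiority rate hardly applies to home-trial ratings. Many laboratory tests measure performance, such as speech reception thresholds, where expectation is a weaker concern.

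Two further inferences go too far. One is that mixing the principle with other device differences is itself a fault. Section 11.1 makes comparison with previous hearing systems an intended aim, and that question is separate from blinding. The other is that on versus off within the new device must become the primary contrast. Section 4.2 allows either reference, and on versus off cannot answer novel versus previous.

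**Conclusion.** The point holds in a limited form. Where two instruments with distinguishable housings are compared, the plan withholds information but neither masks the devices nor checks what participants believed, so the participant blinding claimed in 6.1 and 6.2.2 is not secured. The inferential exposure is narrow: laboratory ratings and preferences, across devices, with mismatched housings. Those can be primary outcomes. Home-trial ratings are exposed too, but mainly as description. Comparisons within one instrument are not affected.

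The size of the bias is unknown. The 13-16% at a shift of 0.2 SD depends wholly on that assumed shift, and the larger table values follow only from assuming larger shifts. They show that a modest expectation effect would matter at n = 20-25; they do not estimate one. The documents do not say how cross-device ratings will be worded in reports, so the fault is an over-broad claim with no stated limit, not a demonstrated misreporting.

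**What to change.** - In 6.2.2, and in the general single-blind sentence of 6.1, limit the blinding claim to comparisons within one instrument or between instruments whose housings cannot be told apart.
- Report rating and preference outcomes from mismatched-housing comparisons as not fully blinded, and do not present them as blinded superiority of the principle.
- Where a sub-study already tests the new device with the principle off or at its weakest setting, as 8.1.2 allows, report that result alongside as the blinded contrast. No extra condition is needed.
- Ask participants once, after all ratings are complete, which device they believed was newer, and report the answers. Asking after each period would itself signal that one device is newer before the next is rated.

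The cost is one extra question, some wording, and a less favourable description of cross-device rating results. No added visits or test conditions are required.
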